5.1. Pre-study

Individuals with a clinical diagnosis of idiopathic pulmonary fibrosis (as defined by the WHO and the Thoracic Society) will be solicited for participation in this phase 3 trial. After signing the informed consent, participants will be randomly assigned to either the placebo or drug groups in a double-blinded randomized fashion. On pre-study day 1 (Screening Visit), and, after signing the informed consent, they will have their degree of nasal inflammation and erythema, nasal cellular morphology, SaO₂, and FEV₁, and FVC levels recorded (baseline). All subjects will have a blood sample taken, and women of child-bearing age will provide a urine sample. The subjects will fill out a quality of life questionnaire (chronic respiratory disease questionnaire (CRDQ), and they will be given a data logbook in which they will record the number of coughs they experience each day for 7 days until they return to the clinic to begin the study (baseline). Any subject who is not compliant $\geq 80\%$ will not be entered into the trial.

Blood will be analyzed for CBCs, and for standard clinical variables, including urea nitrogen, serum creatinine, total protein, serum albumin, total globulin, albumin/globulin ratio, total bilirubin, alkaline phosphatase, aspartate aminotransferase (AST or SGOT), Alanine Aminotransferase (ALT or SGPT), Lactate Dehydrogenase (LDH), Gamma-glutamyl Transferase (GGT), Serum Sodium, Potassium, Chloride Serum, Carbon Dioxide, C-reactive protein, and Total Cholesterol:HDL Ratio to determine organ health. Subjects may not enter the study until the blood and urine samples are analyzed and evaluated to confirm that subjects do not have a metabolic abnormality that would prevent entry, and that women are not pregnant.

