5.2. Study Days

Following the 7-day pre-study period, which includes time for analysis of the blood and urine, eligible IPF patients will return to the clinic and be admitted to the 21-day study. On the first day of the study, these patients will have a physical exam and their vital signs will be recorded. Then, their degree of nasal inflammation and erythema will be evaluated and recorded as before, as will their SaO2, FEV1 and FVC levels and frequency of coughing. Patients will be instructed on how to self-administer their first dose of the nasal spray drug (0.2% sodium pyruvate in 0.9% sodium chloride solution) by first forcefully expelling air from their lungs, and

then spraying 3 squirts of the drug into each nostril, and then forcefully inhaling the drug so that the drug is inhaled into the lungs. After 1 hour, the subjects will have their vital signs taken again. Efficacy and safety evaluations will occur at this 1-hour time period, too, and then again at 2 and 3 hours. The subjects will fill out the product evaluation questionnaire, be given a daily data log form and be given enough drug to last for 21 days (3 bottles), and released from the clinic.

For the next 21 days, subjects will self-administer 3 squirts per nostril of the nasal spray, as instructed, 3 times daily; upon wakening, noon/midday, and before bedtime, Additionally, they will fill out the Daily Data Log form each day to record the number of daily coughs. Patients will be contacted by phone every 2 days to review symptoms and protocol compliance.

On days 8, 14 and 22, they will return to the clinic and have their blood analyzed, vital signs taken, and their degree of nasal inflammation, erythema and cellular morphology recorded. As before, they will be tested for FEV_1 , FVC and SaO_2 levels. The number of coughs they experienced and other information will be discussed with the clinician. They will fill out the product evaluation questionnaire and the CRDQ, and they will then be released from the study on day 22. These data will then be evaluated.

6. Criteria for Patient Selection, Exclusion of Patients, and Number of Patients 6.1. Subject Selection and Number of Patients to be Studied

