6.4. Inclusion of Women and Minorities

Every attempt will be made to include all genders and minorities that present with pulmonary fibrosis and are not exempted due to exclusion criteria.

7. Study Design

Assignment of Subject Number and Randomization

This is a randomized placebo-controlled double-blinded trial. Upon enrollment, each subject will be sequentially issued a unique subject number starting at 100. Once a number has been assigned to a subject, it cannot be re-assigned to another subject. Subjects will be encouraged to complete the study, although they may withdraw at any time without prejudice. Termination will be reported to the sponsor in a timely manner. Details of the reason(s) why a subject was dropped or withdrew from the study will be documented. Enrollment will continue until the number of subjects specified in the protocol has been attained. The data from all subjects that have been given a study compound will be retained for analysis.

8. Randomization

The subjects will be randomized to the placebo control or N115 drug study groups using a random number set.

9. Telephone Communication

Subjects will be instructed to call the clinic should they be experiencing any self-perceived adverse events, or if they have any study-related questions. All telephone information will be documented.

10. Products Description (How Administered)

The product is an all-natural patented 0.2% sodium pyruvate in 0.9% sodium chloride nasal spray solution, pH 7.2, with 0.02% benzalkonium chloride as a preservative. The patient will be instructed on the use of the nasal spray prior to the start of the clinical trial. The plastic bottle contains 30 mL. It is non-steroidal. Patients will forcibly expel air from their lungs and then will administer 3 sprays per nostril while inhaling strongly so that the drug is transported through the nose and into the lungs. The drug is to be administered 3 times per day (morning, mid-day, and evening). The product comes with instructions for administration (3 sprays per nostril).

11. Concomitant Therapy

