13.2. Safety Testing

- Physical Exam
- Vital Signs
- Weight
- Blood pressure
- Pulse
- Temperature
- Blood analysis
- Complete blood count (CBC)
- Clinical tests, including:
 - Urea nitrogen: serum creatinine: total protein: serum albumin: total globulin: albumin/globulin ratio: total bilirubin: alkaline phosphatase: aspartate aminotransferase (AST or SGOT): alanine aminotransferase (ALT or SGPT): LDH: GGT: serum sodium: potassium: chloride serum: carbon dioxide: total cholesterol:hdl ratio:
- Urine test for women of child-bearing age

- Efficacy tests
 - o Nasal examinations by a rhinoscope fitted with a camera
 - \circ FEV₁, FVC

14. Withdrawal Criteria

The patients can withdraw from the study at any time, and for any reason. All data collected from these patients will be analyzed. Reasons for withdrawal will be recorded to insure that it was not due to an adverse event.

The subject has the right to withdraw from the study at any time.

The subject will be withdrawn from the study if:

- There is deterioration in the subject's signs and symptoms and/or the subject develops a disease or condition that, in the opinion of the investigator, would compromise the subject's safety by continuing in the study.
- In the investigator's judgment, it is in the best interest of the subject.
- There is a violation of the protocol inclusion and/or exclusion criteria, as deemed relevant by the investigator and discussed with the medical monitor.
- The subject begins to take any medication(s) that is(are) excluded by the protocol.
- Any of the conditions for stopping rules are met.

If a subject withdraws prematurely from the study due to the above criteria or any other reason, study staff should make every effort (at withdrawal) to complete the full set of evaluations listed for the early termination/end-of-study visit. The reason for subject withdrawal must be documented in the case report form (CRF).

If a subject withdraws from the study due to an adverse event (AE) (eg, clinical signs, symptoms, or clinically significant laboratory abnormality), the subject will be asked to return to the clinic, at a minimum, for the evaluations scheduled for the posttreatment follow-up period. If the AE has still not resolved, additional follow-up will be performed, as appropriate, and documented in the subject's medical records. As a minimum requirement, AEs should be followed for 30 days after the subject's last dose of study medication.

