20.2. Data Collection, Management, and Statistical Analysis

The data management staff at the research clinic will collect and manage the data. Data will be obtained, maintained, and transmitted securely in accordance with HIPAA guidelines. Monitoring and auditing of the data will be conducted by a staff member of Cellular Sciences.

Statistical analysis will be performed on deidentified data. The basic statistical analysis will be repeated measurements of Analysis of Variance using baseline measurements as a covariant (ANCOVA). Age, sex, time since initial diagnosis with IPF, concurrent medications and smoking status are considered potential covariates. Number of coughing episodes reported for a 24-hour pre-study period, and other pre-study data information, will be compared to the data collected during the trial. The differences between baseline data and the data collected during the trial will be compared and analyzed (Within treatment). Additionally, the data of the patients on the experimental therapy will be compared to the data generated by the patients on placebo (Between treatments). P values of <0.5 will be considered significant. FEV1 and FVC will similarly be analyzed as secondary outcome measurements. Relative changes will be analyzed by JMP, Matillion, XLSTAT or R software by [name] or [name], who will be responsible for the statistical analysis.

Partial patient data will be included in the statistical analysis if patients withdraw from the study, but data from non-compliant patients will be excluded. Our previous research (REF) indicates that a sample size of 20 is sufficient to detect a statistically significant difference (p<0.05) between treatment groups. We have chosen to enroll 25 patients in each treatment group to ensure we achieve the necessary sample size, taking into account that some patients may not complete the study, and some data will be incomplete or excluded from the study.

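### The plan drops undefined non-compliant patients in section 20.2 but keeps every dosed subject in section 7, so the primary analysis set is not fixed

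*Combined protocol and SAP*

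**What the plan says.** Four places in the combined protocol and SAP bear on who is analysed.

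- Section 20.2 first sets a rule for withdrawals: "Partial patient data will be included in the statistical analysis if patients withdraw from the study". The second half of that sentence then takes another group out: "but data from non-compliant patients will be excluded". The sample-size margin in the same section allows for this: "some patients may not complete the study, and some data will be incomplete or excluded from the study".
- Section 7 (Study Design): "The data from all subjects that have been given a study compound will be retained for analysis".
- Section 14 (Withdrawal Criteria), on patients who withdraw: "All data collected from these patients will be analyzed". The same section lists as a reason for withdrawal: "The subject begins to take any medication(s) that is(are) excluded by the protocol".
- Section 20.3: data collected up to withdrawal stay in the database.

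Three places bear on compliance.

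- Section 5.1: a subject less than 80% compliant in the 7-day pre-study period "will not be entered into the trial". What is measured is not stated.
- Section 5.2: "Patients will be contacted by phone every 2 days to review symptoms and protocol compliance". No cut-off is attached.
- Section 18: the logbook is described as capturing coughs, adverse events and medication changes. Doses taken are not listed.

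No intention-to-treat, per-protocol or other analysis set is named.

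**The concern.** A dosed patient who is later judged non-compliant is kept for analysis under section 7 and removed under section 20.2. A patient who is both withdrawn and non-compliant, for example one who started an excluded medication, is included by the first half of the section 20.2 sentence and by section 14, and excluded by the second half. No order of precedence is given.

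The excluding term is also undefined. It could mean missed doses, missed diary days or prohibited medication, and each reading removes different patients.

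Two things are at stake. Compliance is observed after randomisation, so excluding on it can bias the between-group comparison in either direction if it is related to outcome differently in the two arms. And if the set is not fixed in advance, it can be chosen after results are seen, which raises the false-positive rate even when both arms behave alike.

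**Working it through.** **The plan's own figures.** Section 20.2 says a sample size of 20 is enough and enrols 25 per group. If 20 is per group (not stated), 20 / (1 − 0.20) = 25, so the margin is up to five per group, or 20%. It covers non-completion, incomplete data and exclusion together, so five exclusions per arm is an upper-end figure. The 20 itself cannot be reproduced: no power, SD or linked effect size is given, and its source is a blank reference.

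**The rules side by side.**

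| Patient | Section 7 | Section 14 | Section 20.2 |
|---|---|---|---|
| Dosed, compliant, completes | keep | not addressed | keep |
| Dosed, withdraws, compliant | keep | analyse | keep |
| Dosed, non-compliant, completes | keep | not addressed | exclude |
| Dosed, non-compliant, withdraws | keep | analyse | keep and exclude |

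**A concrete case.** Section 5.2 asks for the daily log over 21 days; the footnote to the testing schedule in section 13.1 ends it at day 14. If someone applied the 80% entry figure to diary days (an assumption), a patient who followed the footnote would score 14/21 = 67% and could be excluded.

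**Size of the bias.** The documents give no rate of non-compliance and no link to outcome, so this is illustration. Inputs: no drug effect; 25 per arm; outcome Y standard normal, higher meaning worse cough; latent non-compliance L = rY + √(1 − r²)·e; the 2 or 5 patients with the highest L removed from each arm; pooled two-sided t test at 0.05; 100,000 trials per scenario. The 0.05 is the level in the sample-size sentence of section 20.2; the 0.5 printed elsewhere in that section is a separate issue.

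Since E(Y | L) = rL, the expected bias towards N115 is (r on N115 − r on placebo) × c, where c is the shift in an arm's mean when r = 1: 0.152 SD for 2 of 25 removed and 0.336 SD for 5 of 25. For example, (0.5 − 0.3) × 0.336 = 0.07 SD and 0.5 × 0.336 = 0.17 SD.

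| r on N115 / placebo | 2 excluded per arm: bias, rejection | 5 excluded per arm: bias, rejection |
|---|---|---|
| 0.5 / 0.5 | 0.00 SD, 5.6% | 0.00 SD, 5.8% |
| 0.7 / 0.7 | 0.00 SD, 6.1% | 0.00 SD, 6.9% |
| 0.5 / 0.3 | 0.03 SD, 5.4% | 0.07 SD, 6.1% |
| 0.5 / 0 | 0.08 SD, 6.1% | 0.17 SD, 8.6% |
| 0.7 / 0 | 0.11 SD, 7.0% | 0.24 SD, 12.7% |
| 1.0 / 0 | 0.15 SD, 9.4% | 0.34 SD, 22.8% |

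With r = 0 in both arms, bias is 0.00 and rejection 4.9% to 5.0%, as it should be. A relation on placebo only gives bias of the same size against N115. Monte Carlo standard error is about 0.08 percentage points at 6% and 0.13 at 23%.

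**Baseline adjustment.** The plan uses repeated-measures ANCOVA; a single-endpoint ANCOVA with five excluded per arm is a simplification of it. The first three rows of the table are the similar-arms case, the last three the N115-only case.

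| Baseline–outcome correlation | Similar in both arms | N115 only |
|---|---|---|
| 0.5 | 0–0.05 SD, 5.5–6.4% | 0.13–0.27 SD, 7.5–18.5% |
| 0.7 | 0–0.03 SD, 5.3–6.0% | 0.09–0.19 SD, 7.0–14.6% |

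**Choosing the set afterwards.** Both arms alike, r from 0 to 0.7, trial counted positive if any candidate set gives p < 0.05:

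- all patients, or 2 excluded per arm: 6.4–6.9%
- all patients, or 5 excluded per arm: 7.2–8.2%
- four cut-offs (0, 2, 5 or 8 per arm): 9.4–10.7%

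**The case against.** The strongest reply is that the sections can be reconciled. Section 7's sentence sits in a paragraph on subject numbering and withdrawal and could be about keeping data, as in section 20.3. Section 20.2 is the statistical section and anticipates exclusions twice, so the specific rule would limit the general one. This makes the conflict less stark but does not remove it: section 7 says the data are kept for analysis, and section 20.3 already covers the database. Even if section 20.2 prevailed, the excluded group would still be undefined.

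The next reply is size. In the ordinary case the effect is modest. The large figures need a relation in one arm only or a free choice of cut-off, and every correlation and count is assumed. That stands. Blinding of subjects and investigators, with indistinguishable products, makes deliberate arm-dependent exclusion less likely. It does not prevent the arms differing in who becomes non-compliant, and nothing requires classification before unblinding. Nor does the text say classification happens afterwards; it is silent.

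Two smaller points also stand. Section 5.1 places random assignment after consent, before the 7-day logbook, so the 80% rule may itself remove randomised patients, and a set limited to dosed patients would not show them. And a few pages, including material just before section 5.1, were missing from the text available, so a definition there cannot be ruled out; sections 7, 14, 18 and 20, where one would belong, have none.

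**Conclusion.** The concern holds and must be fixed. Confidence is high on two textual facts: sections 7 and 20.2 give opposite instructions for a dosed, non-compliant patient, and on-treatment non-compliance is not defined in the text reviewed. With 25 per group each exclusion is 1/25 = 4% of an arm, withdrawn subjects are not replaced, and an analysis set left open cannot be repaired convincingly after unblinding.

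The numerical consequence is uncertain because the documents supply no inputs. A reasonable reading is little bias and a small excess of false positives if the arms behave alike, and a material distortion, in either direction, only if non-compliance tracks outcome in one arm and not the other. The severity rests on a primary analysis that cannot be carried out unambiguously and on a post-randomisation exclusion, not on the worst simulated case.

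**What to change.** Replace the exclusion in section 20.2 and bring sections 7 and 14 into line. Suggested wording:

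> The primary analysis includes all randomised patients who received at least one dose, in their assigned group, with all available data regardless of compliance.

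Then:

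- Keep the compliant-only analysis as a sensitivity analysis.
- Define on-treatment compliance numerically, separately for missed doses, missed diary entries and prohibited medication, and name the data source for each.
- Classify patients, and document it, before unblinding.
- Report by arm any randomised patient removed before the first dose, including under the 80% rule.
- Reconcile the diary period in section 5.2 with the footnote in section 13.1 before any diary-based definition is used.

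The cost is mainly protocol wording, with no extra patients or visits. A dose record has to be named if missed doses are to be classified, since the logbook as described does not hold one. The downside is small: non-adherence may slightly dilute the estimated effect, and the compliant-only result remains available beside it. The change does not recover diary data that were never recorded.

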20.3. Data from Patients who Withdraw from the Study

If a subject withdraws from a study, the data collected on the subject to the point of withdrawal will remain part of the study database and will not be removed.

The investigator may ask a subject who is withdrawing whether the subject wishes to provide continued follow-up and further data collection subsequent to their withdrawal from the interventional portion of the study. Under this circumstance, the discussion with the subject would distinguish between study-related interventions and continued follow-up of associated clinical outcome information, such as medical course or laboratory results obtained through non-invasive chart review and address the maintenance of privacy and confidentiality of the subject's information.

If a subject withdraws from the interventional portion of the study but agrees to continued follow-up of associated clinical outcome information as described in the previous paragraph, the investigator must obtain the subject's informed consent for this limited participation in the study (assuming such a situation was not described in the original informed consent form). In accordance with FDA regulations, Institutional Review Board (IRB) approval of informed consent documents would be required (21 CFR 50.25, 56.109(b), 312.60, 312.66, 812.100).

If a subject withdraws from the interventional portion of a study and does not consent to continued follow-up of associated clinical outcome information, the investigator must not access for purposes related to the study the subject's medical record or other confidential records requiring the subject's consent. However, an investigator may review study data related to the subject, collected prior to the subject's withdrawal from the study, and may consult public records, such as those establishing survival status.

21. Product Packaging

The product packaging will comply with FDA regulations. The nasal spray will be contained in a sterile plastic vial that can be squeezed to administer the correct dosage. The vials necessary for each study period (i.e. 14 days) will be placed in a paperboard box in a plastic bag with the patient's number.

22. Product Storage Requirements

At Research Center

The products will be stored at room temperature, but not above 85°F.

In Home

The products will be stored at room temperature, but not above 85°F.

23. Record Retention

All records will be kept by the clinic for a period of 3 years. After that they will be sent to Cellular Sciences.

24. Reports on Adverse Events

All Adverse Events, as defined below, will be recorded, evaluated and reported in accordance with 21 CFR 312.32. These Adverse Events may occur during the study or after the study has completed.

24.1. Definition of an Adverse Event

Adverse event means any untoward medical occurrence associated with the use of a drug in humans, whether or not considered drug related.

Life-threatening adverse event or *life-threatening suspected adverse reaction*. An adverse event or suspected adverse reaction is considered "life-threatening" if, in the view of either the investigator or sponsor, its occurrence places the patient or subject at immediate risk of death. It does not include an adverse event or suspected adverse reaction that, had it occurred in a more severe form, might have caused death.

Serious adverse event or serious suspected adverse reaction. An adverse event or suspected adverse reaction is considered "serious" if, in the view of either the investigator or sponsor, it results in any of the following outcomes: Death, a life-threatening adverse event, inpatient hospitalization or prolongation of existing hospitalization, a persistent or significant incapacity or substantial disruption of the ability to conduct normal life functions, or a congenital anomaly/birth defect. Important medical events that may not result in death, be life-threatening, or require hospitalization may be considered serious when, based upon appropriate medical judgment, they may jeopardize the patient or subject and may require medical or surgical intervention to prevent one of the outcomes listed in this definition. Examples of such medical events include allergic bronchospasm requiring intensive treatment in an emergency room or at home, blood dyscrasias or convulsions that do not result in inpatient hospitalization, or the development of drug dependency or drug abuse.

Suspected adverse reaction means any adverse event for which there is a reasonable possibility that the drug caused the adverse event. For the purposes of IND safety reporting, "reasonable possibility" means there is evidence to suggest a causal relationship between the drug and the adverse event. Suspected adverse reaction implies a lesser degree of certainty about causality than adverse reaction, which means any adverse event caused by a drug.

Unexpected adverse event or unexpected suspected adverse reaction. An adverse event or suspected adverse reaction is considered "unexpected" if it is not listed in the investigator brochure or is not listed at the specificity or severity that has been observed; or, if an investigator brochure is not required or available, is not consistent with the risk information described in the general investigational plan or elsewhere in the current application, as amended. For example, under this definition, hepatic necrosis would be unexpected (by virtue of greater severity) if the investigator brochure referred only to elevated hepatic

enzymes or hepatitis. Similarly, cerebral thromboembolism and cerebral vasculitis would be unexpected (by virtue of greater specificity) if the investigator brochure listed only cerebral vascular accidents. "Unexpected," as used in this definition, also refers to adverse events or suspected adverse reactions that are mentioned in the investigator brochure as occurring with a class of drugs or as anticipated from the pharmacological properties of the drug, but are not specifically mentioned as occurring with the particular drug under investigation.

